5. STUDY DESIGN

We will use a multi-site randomized controlled trial (RCT) to evaluate the effects of counter attitudinal advocacy (CAA) relative to assessment only (AO) control on drinking and related problems among college students, and the relative effects of CAA vs. PNF on relevant drinking outcomes. Eligible students will be randomly assigned to one of 3 conditions (personalized CAA or PNF or AO control). Hypothesized mechanisms of change (alcohol-related attitudes and dissonance, perceived drinking norms) will be evaluated immediately after the intervention (posttest) and drinking outcomes (drinks per week, heavy drinking frequency, peak BAC, alcohol-related problems, PBS) will be evaluated at 1-, 3-, and 6-months post-intervention. All procedures are conducted for the purpose of research only.

We propose to conduct this study at two sites (both Carnegie Tier 1 Research universities) that have distinctly different campus and student profiles in order to explicitly test hypotheses about the differential efficacy of CAA vs PNF in different campus contexts. Brown University is a private residential 4-year college with approximately 6200 undergraduates (51% female and 43% minority) and characteristics associated with higher risk of alcohol misuse (e.g., Northeast region, Greek system, athletic tradition). All first- and second-year students and most third-year students live together in on-campus dorms. Students at Brown report high rates of drinking: 81% of Brown students drank in the past 3 months, and 51% report binge drinking in the last two weeks. In contrast, the University of Houston (UH) is a large public research university serving more than 34,716 undergraduate students (51% female and 74% minority). Roughly 80% of UH students live off campus. Located in America's fourth-largest city, UH was designated as the most ethnically diverse metropolitan research university in the United States by Forbes in 2010. UH students report a below average drinker profile, with 45% of the students reporting current drinking and 23% report binge drinking in the last month. Overall, the base rates for any drinking and binge drinking are lower at UH than at Brown. These two sites allow us to test the comparative efficacy of CAA vs PNF in contexts with both high and low base rates of heavy drinking. If site does not moderate efficacy, then the replication of the effects of CAA across sites will provide evidence of generalizability of observed effects.

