6. STUDY POPULATION

6.1. Target Sample. The target sample for analyses is $N=600$ college student drinkers: 300 from Brown University, and 300 from the University of Houston. We will randomize 100 eligible students from each site to the CAA ($n=200$), PNF ($n=200$), and AO ($n=200$) conditions.

6.2. Inclusion Criteria. Inclusion criteria are:

(1) **Age 18-26.** The age range of 18-26 (a) coincides with the distinct developmental period of “emerging adulthood” (Arnett, 2005), (b) is characterized by a high prevalence of heavy episodic drinking (Johnson et al., 2012), and (c) is representative of college students, the majority of whom are 26 years of age or younger (Digest of Education Statistics: 2012).

(2) Male or female student at Brown University or University of Houston. The present study represents a first step in using counter-attitudinal advocacy activities in an attempt to reduce risky drinking behavior. As such, we focus on college students because they exhibit high rates of heavy episodic drinking (Johnson et al., 2012), and their identification with other college peers facilitates the testing of the enhanced manipulation. We recruit at 2 sites that differ in drinking patterns and demographics and geographic location to evaluate the generalizability of the study findings. The findings could have implications for alcohol abuse prevention both with college students and young adults more broadly.

(3) Past month heavy episodic drinking (for men, ≥ 5 drinks in one day, for women ≥ 4 drinks in one day). The 4/5 drink cutoff has been widely used as an indicator of risk ([name], Larimer, & Lewis, 2004; Wechsler & Nelson, 2001) and as a screening criterion in intervention studies targeting heavy drinking students. Our preliminary studies show that heavy drinking frequency is significantly correlated with attitudes towards moderate ($r = -.42$) and heavy ($r = .45$) drinking. By including only drinkers who have reported heavy episodic drinking we optimize the likelihood that developing arguments in favor of moderate drinking ($<4/5$ drinks/occasion) will constitute counter-attitudinal advocacy, and create dissonance between the espoused attitude in favor of moderation and recent behavior.

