9.1.4. Hypothesized mediators

Attitudes toward moderate consumption and attitudes toward heavy consumption will be assessed with measures modified from previous research (Hagger et al., 2012; Norman, 2011). For moderate consumption, the stem will read, "Keeping my alcohol drinking within what is considered moderate drinking for adults (i.e. at 4 or fewer drinks for men or at 3 or fewer drinks for women) on each individual occasion over the next month would be..." For heavy consumption, the stem will read, "Having five or more drinks (for males)/four or more drinks (for females) in a sitting over the next month would be..." For both measures, there are five semantic differential scales that range from 1 to 5: unenjoyable-enjoyable, bad-good, harmful-beneficial, foolish-wise, and unpleasant-pleasant. To test AIM 3, changes in attitudes toward heavy drinking and attitudes toward moderate drinking are anticipated to serve as a mediator of the CAA (but not PNF) intervention effects.

Cognitive dissonance will be assessed using the Dissonance Thermometer (Devine, Tauer, Barron, Elliot, & Vance, 1999; Elliot & Devine, 1994; Simmons & Brandon, 2007; Simmons et al., 2004; Simmons, et al., 2013). Items include asking participants how uncomfortable, angry at themselves, shameful, uneasy, friendly (reverse scored), disgusted with themselves, embarrassed, bothered, optimistic (reverse scored), annoyed at themselves, disappointed at themselves, happy (reverse scored), energetic (reverse scored), and good (reverse scored) they feel immediately following the CAA activity. The 3-item affective discomfort factor has been found to be susceptible to cognitive dissonance inductions resembling our CAA procedure, with other target behaviors (Devine et al., 1999; Simmons et al., 2013). In Aim 3 we will test dissonance as a mediator of both CAA and PNF interventions.

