Perceived descriptive norms will be measured by a modified version of the Drinking Norms Rating Form (DNRF; Baer et al., 1991). The gender-specific version (Lewis & [name], 2004) assesses perceived typical number of drinks consumed per drinking occasion (e.g., "how many drinks on average do you think a typical male/female Brown/UH student consumes on a given occasion?"), and perceived frequency of drinking occasions (e.g., "how often do you think a typical male/female Brown/UH student consumes alcohol?"). The DNRF assesses perceived typical weekly drinking by having participants fill in the average number of standard drinks they think the typical (male/female) Brown/UH student consumes for each day of the week over the previous month. The DNRF has been used in multiple studies of college drinking and has shown good concurrent and prospective validity ([name], Dillard, Lewis, Bergstrom, & Neil, 2006). In Aim 3 we test changes in descriptive norms as mediators of the PNF (but not CAA)

effects.

Perceived Injunctive norms will also be assessed using an adaptation of the DNRF shown to be reliably associated with respondent drinking (Krieger et al., 2016). This drink-based injunctive norms assessment includes (a) “maximum number of drinks a typical male/female Brown/UH student approves of consuming on one occasion?”, (b) “maximum frequency of drinking a typical male/female Brown/UH student would approve of in a week?”, and (c) “what is the maximum number of drinks a typical male/female Brown/UH student would consider acceptable to consume on each day of the week?.” [name] et al. (in preparation) recently demonstrated support for personalized injunctive norms feedback based using this measure (see preliminary studies). Additionally, injunctive norms will be assessed for negative consequences of drinking. Rating scales will be used to assess how unacceptable and acceptable experiencing specific drinking consequences is believed to be (Prince et al., 2015). These consequences include driving after drinking, drinking enough to pass out, blacking out due to drinking, etc. In Aim 3 we test changes in injunctive norms as mediators of the PNF (but not CAA) effects.

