Hypotheses associated with Aim 3 will evaluate mediators of intervention effects. We will follow procedures described by MacKinnon and colleagues (e.g., MacKinnon, Fairchild, & Fritz, 2007) to assess mediation. Mediation will test indirect effects using the AB products method with bootstrapped standard errors where A will represent effects of intervention contrasts by time interactions on mediators. B will represent the associations of mediators on subsequent drinking outcomes. Both A and B paths will control for baseline outcomes. Hypotheses associated with Aim 4 will follow a similar approach but will add prospective moderators and products of prospective moderators and contrasts

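### Aim 3 mediation: the B path does not name the baseline mediator or say whether the mediator is a level or a change, so the indirect effect can be inflated when the intervention shifts the mediator

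*Combined protocol and SAP*

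**What the plan says.** Section 10.2 tests indirect effects with the "AB products method with bootstrapped standard errors". The paths are defined in two short statements: "A will represent effects of intervention contrasts by time interactions on mediators" and "B will represent the associations of mediators on subsequent drinking outcomes". The covariate rule follows: "Both A and B paths will control for baseline outcomes".

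Other sections bear on how to read that rule:

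- **Section 10.2, Aim 1.** The list of multiple outcomes includes both attitude measures and dissonance. Perceived norms are not in it.
- **Sections 9.1.2 and 9.1.4.** These separate primary and secondary outcomes from hypothesized mediators.
- **Section 9.1.4.** It describes mediators as changes: "changes in attitudes toward heavy drinking and attitudes toward moderate drinking are anticipated to serve as a mediator". It uses similar language for descriptive and injunctive norms. Dissonance is described as what participants feel just after the activity.
- **Section 5.** Mechanisms are measured at posttest, and drinking at 1, 3 and 6 months.
- **Section 6.2.** In preliminary studies, "heavy drinking frequency is significantly correlated with attitudes towards moderate" drinking (r = -.42) and heavy drinking (r = .45).
- **Section 7.4.** Condition is assigned after the baseline assessment.

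**The concern.** Randomisation protects the effect of arm on the mediator. It does not protect the association between mediator and later drinking. If students who favour heavy drinking at baseline also drink more later, over and above what one baseline drinking measure captures, a posttest attitude score carries that information into B. Multiplied by a real shift in the mediator, this gives a non-zero indirect effect even if changing the attitude does nothing.

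Aim 3 makes discriminating claims: CAA should work through attitudes and dissonance but not norms, and PNF through norms and dissonance but not attitudes. If B is non-zero through prior association, each arm appears to work through whatever it moved. The predicted pattern could then come from the A paths alone.

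**Working it through.** The plan states no sample size, power or error rate for Aim 3, so there is no figure to reproduce. The check asks what the literal B model estimates when the true effect of the posttest mediator is zero.

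**Inputs from the documents.** Baseline correlation r = .45 (Section 6.2). 510 after 15% attrition (Section 10.1), so 510/3 = 170 per arm. An illustrative A of .28 SD (Section 10.1 gives this size for intervention effects, not for mediators).

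**Assumptions not in the documents.** Continuous standardised outcome; arm in the B model; and one of two structures:

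1. *Lagged effect.* Baseline mediator M0 affects later drinking by c = .1-.2 SD; mediator stability s = .5-.7.
2. *Trait plus noise.* Mediator and drinking are stable traits measured with reliability ρ = .6-.8.

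**Formulas for B when the true effect is 0** (1 − r² = .7975)

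- Structure 1, literal model: B = c·s(1 − r²)/(1 − s²r²). For s = .5, the multiplier of c is .39875/.949375 = .420. For s = .7, it is .55825/.900775 = .620.
- Structure 1, with M0 added: B = 0.
- Structure 1, change score instead of level: B = −c(1 − s)(1 − r²)/[(1 − s)²(1 − r²) + 1 − s²], that is −.420c for s = .5 and −.411c for s = .7.
- Structure 2, literal model: B = r(1 − ρ)/(1 − r²). For ρ = .6, .18/.7975 = .226.
- Structure 2, with M0 added: B = r(1 − ρ)/(1 + ρ − 2r²). For ρ = .6, .18/1.195 = .151.
- Structure 2, change score: B = 0.

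**Results.** False mediation is the share of 2,000 simulated trials in which a 95% Monte Carlo interval for A×B, used in place of the bootstrap, excluded zero. Simulated B agreed with the formulas to about .002.

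| Setting | B, literal | A×B = .28B | False mediation, literal | B, M0 added | False mediation, M0 added | False mediation, change score |
|---|---|---|---|---|---|---|
| c .1, s .5 | .042 | .012 | 13% | 0 | 3% | 11% |
| c .1, s .7 | .062 | .017 | 24% | 0 | 4% | 8% |
| c .2, s .5 | .084 | .024 | 38% | 0 | 4% | 34% |
| c .2, s .7 | .124 | .035 | 65% | 0 | 4% | 26% |
| ρ .6 | .226 | .063 | 81% | .151 | 74% | 3% |
| ρ .7 | .169 | .047 | 78% | .104 | 48% | 5% |
| ρ .8 | .113 | .032 | 71% | .065 | 24% | 5% |

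A repeat with A = .30 gave the same picture: 18-53% falling to 4-6% under structure 1, and 77-86% falling to 22-76% under structure 2.

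**Two boundary cases**

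- No lagged effect and no trait structure (c = 0): the first formula gives B = 0 whatever r is. Simulation with r = .45 and A = .30 gave B of about 0 and false mediation in about 4% of trials.
- No shift in the mediator (A = 0): the literal model gave a mean indirect effect of about 0 and false mediation in 0.6-5.2% of trials.

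**A path.** Approximate standard errors at 170 per arm for mediator stability .6 and .8:

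- posttest only: √(2/170) = .108;
- change from baseline: √[(2/170)·2(1 − s)] = .097 and .069;
- baseline mediator as covariate: √[(2/170)(1 − s²)] = .087 and .065.

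A contrast-by-time effect that includes baseline as a time point is the second of these, which is close to the third.

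**The case against.** The strongest reply is that the plan may already include the baseline mediator. The Aim 1 list treats attitudes and dissonance as outcomes, the A path's own outcome is the mediator, and Section 9.1.4 speaks of changes. A reader might infer that the plan definitely leaves the baseline mediator out. The documents do not support that: the text is ambiguous. But the ambiguity is not harmless. Norms, the PNF mediators, are missing from the Aim 1 list. The language of change is not carried into the B model. The table shows that a change score is not a safe default either, since it is biased in the opposite direction under structure 1.

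A reader might also infer that the reported correlations alone would pass as mediation. They would not: with c = 0, B is zero. The correlations make a residual association plausible but do not show it, and they concern attitudes only, not norms or dissonance.

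Nor do the documents support a claim that the A path is biased. Arm is randomised after baseline, and A is a contrast-by-time effect. At most some precision is lost, and little if baseline is one of the time points.

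Finally, part of the timing is already there. Mechanisms are measured at posttest and B refers to later drinking. What is missing is a statement of which mediator occasion enters B.

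**Conclusion.** The concern holds as a gap in the B path. The plan does not say whether the mediator is a level or a change, nor that its baseline value is adjusted for. If it is not, and if the baseline mediator predicts later drinking beyond baseline drinking, B is inflated. The indirect effect can then appear significant whenever the intervention moves the mediator.

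The direction of the bias under those conditions is firm. The size is not: spurious indirect effects of about .01-.06 SD and the false-mediation rates above depend on assumed lagged effects, stabilities and reliabilities, and on a continuous outcome where the plan assumes negative binomial counts. Adding the baseline mediator removes the bias under structure 1 and only reduces it under structure 2. The point should be settled before the Aim 3 analysis; it does not touch the tests for Aims 1 and 2.

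**What to change.** Replace the covariate sentence in Section 10.2 with a specification along these lines:

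*A path: effect of the intervention contrast on the posttest mediator, with the baseline mediator in the model as a time point or covariate. B path: outcome at 1, 3 and 6 months on the posttest mediator, adjusting for arm, the baseline outcome and the baseline value of the same mediator (attitudes, descriptive norms, injunctive norms).*

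Then:

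- Define the term baseline outcomes separately for each path.
- State how dissonance is handled. Section 9.1.4 describes only feelings after the activity, so it is unclear whether a comparable baseline score exists. If none does, say so and label the dissonance result as more exposed to this bias.
- Add a sensitivity analysis for residual mediator-outcome confounding, for example how large a residual correlation between mediator and outcome would bring the indirect effect to zero.

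**Cost.** This is a change of analysis wording and one sensitivity analysis. Attitudes and norms are listed under the baseline assessment (Section 9.1.4), so no new data collection appears to be needed for them. Dissonance is the one mediator for which this needs checking.

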11. RISK/BENEFIT ASSESSMENT

11.1. Possible Risks. The level of risk that our volunteer participants will be exposed to by completing online surveys of their drinking practices and related cognitions, or by engaging in writing or computer feedback activities about promoting safer drinking practices on campus is minimal. The main risks of participation include (a) a breach of confidentiality or (b) discomfort or distress answering questions about drinking behavior and/or consequences.

Confidentiality could be breached by research staff or if data stored electronically were accessed by an unauthorized source. The seriousness of the consequences of a breach of confidentiality would depend on the nature of the information revealed and to whom the information was revealed. Some participants will be under the legal drinking age of 21, and will be reporting past episodes of underage drinking. However, this is a relatively small risk because, as a general rule, reports of past drinking carry minimal legal liability because of the difficulty in proving the behavior after the fact. Given the numerous steps we take to protect participant confidentiality (as described below), we think the risk of a breach of confidentiality is low.

Participants may feel uncomfortable or distressed answering questions about their drinking behavior on surveys. Participants will have been informed of the types of questions they will be asked to answer, and they likely would not choose to participate if these types of questions made them feel uncomfortable. Participants have the option of refusing to answer the questions or withdrawing from the

study if they think the questions are too personal. In our previous research using similar survey questions with thousands of college students, none of the participants reported being significantly distressed by the questions. At each assessment point, participants will have the option to download a Resource Sheet with contact information for substance abuse and mental health services (see Appendix C, Mental Health Safety Plan).

11.2. Protection against Possible Risks

Minimization of risk -- Confidentiality. Several steps will be taken to ensure that data remain confidential. These steps have successfully maintained confidentiality in our previous work with college student drinkers.

- (a) Identification numbers.** All participants will be assigned a unique study identification (ID) number upon enrollment, and the study ID will be the only identifier linked to participant responses on the online surveys and digitized audio versions of the orally delivered CAA essays and PNF feedback sessions. For participants in the RCT this ID number will be the only identifier in the database containing participant responses; the study ID number will be stored electronically in a tracking database with contact information and used to link the baseline, posttest, and follow-up surveys. The tracking database will be stored on a password-protected computer, and only study personnel will have access to the database linking names, contact information, and ID numbers. All identifying information will be destroyed upon completion of data collection.
- (b) Data storage.** All data will be stored electronically on secure servers by Qualtrics and then downloaded to the secure server at the Brown Center for Alcohol and Addiction Studies. A password will be required to access data that are stored electronically, and only personnel involved with the project will have access to the electronic data. In the RCT, names and identifying information required for follow-up reminders and follow-up payments will always be kept separate from research data. The data generated in the RCT will remain confidential until the final follow-up is completed, and then identifying information will be removed and the data de-identified.
- (c) Staff training.** All study staff will receive training in maintaining confidentiality. Training will focus on procedures for making sure data are not accessed by individuals outside of the research team, keeping identifying information separate from data, and not disclosing participant information or participant names to individuals outside of the research team. All staff will complete an online CITI ethics training, and will sign an agreement to keep all research information confidential. When hiring project staff, we will recruit individuals with previous research experience who demonstrate understanding of the importance of confidentiality and research ethics and convince the research team of their high personal integrity.
- (d) Presentation of published data.** Quantitative data will be published in aggregate form only. Data from individual participants will not be identifiable in reports or manuscripts.

Minimization of risk -- Distress. We will take several steps to reduce the possible discomfort or distress participants may feel about answering the survey questions or participating in the experimental manipulations.

- (a) Screening questions and study clearly explained.** Before answering screening questions, participants will be informed that responses are confidential, and they will only be used to identify who is eligible to proceed to consent to the study. None of the screening questions will be set to “force response” in Qualtrics, but if key eligibility criteria are skipped, the student will see a pop-up message acknowledging that they can’t be determined to be eligible or not if the item is skipped. For those who are eligible, a detailed explanation of the study, including what study participation would involve, the nature of the questions participants will

be asked to answer, their right not to answer any question, the structure of the in-person session, and the right to withdraw from the study at any time without penalty will be provided to the participants, both in writing (through the informed consent form) and verbally (by the RA). Participants will be encouraged to ask questions about the study. Participants who are uncomfortable answering these types of questions or participating in this type of intervention can choose not to participate. Those who elect to participate but are uncomfortable with the procedures can choose to withdraw from the study.

- (b) **Privacy.** Participants will also have the right to decide what they want to reveal about themselves. Participants will be told they have the right to refuse to answer any survey question, and they do not have to engage in any personal discussions that they are uncomfortable with during the experimental procedures.
- (c) **Referrals.** At the end of each online survey (at baseline and all follow-ups), participants will be provided with a list of counseling centers and alcohol and drug resources, including ones both inside and outside of the university, and the phone number for a 24-hour crisis hotline.
- (d) **Staff training.** We will hire staff with strong interpersonal and communication skills and the ability to empathize with others. Study team members will receive extensive training in respectful treatment of human subjects (i.e., CITI certification) and close supervision from [name] (a licensed clinical psychologist) and Drs. [name] and [name], all experienced researchers.

11.3. Expected Benefits. The research may directly benefit **participants** in several ways. First, in our previous research with college students, participants frequently report that they enjoyed completing self-report surveys that increase their awareness of their health behaviors. Some also report that completing the surveys led to their engaging in fewer health-risk behaviors. Second, participants who receive the counter attitudinal advocacy manipulation or the personalized normative feedback are expected to benefit from these “interventions” and reduce their risk of heavy episodic drinking. Third, some participants will find participating in the research is fulfilling because it affords them an opportunity for altruism, that is, they appreciate the chance to contribute to a prosocial activity that may help others like themselves reduce their risk of alcohol-related consequences.

The study will also benefit **the public health community and society in general**. Indeed, the overall goal of the research is to develop an intervention that will help college students to avoid drinking related-harms (injury, assault, property damage) to themselves and to others. Based on our findings, campus communities may be better prepared to prevent the onset of risky drinking practices.

